6.3.2 Initial Escalation Period

6.3.2.1 Day 1

The Initial Escalation Day 1 visit should occur within 10 days of the Screening DBPCFC Day 2 and must occur within 6 weeks (preferably by Day 29) following signing of the consent/assent form. If the Initial Escalation is not started in this time frame, written approval to rescreen the subject and/or to waive any of the Screening procedures must be obtained from the sponsor's medical monitor.

A physician must be available at all times during the CRC dosing visits. Subjects must be free from active wheezing or a flare of atopic disease (eg, atopic dermatitis), or suspected intercurrent illness prior to initiating IP dose escalation. Additionally, subjects must be fully recovered (ie, back to their baseline state of health), from any preceding illness for at least 3 days, depending on the investigator-determined severity of the illness.

The following assessments/procedures will be performed during the Initial Escalation:

Day 1 visit in the CRC:

- Concomitant medication update
- Complete physical examination, including weight
- Diet (food allergen exposure) history update
- Pre-dose vital sign measurement (BP, pulse rate, body temperature)
- PEFR (3 attempts are to be performed, and the best value taken). PEFR should be measured at the same time of day for each visit assessment (eg, morning, afternoon, evening).
- Administration of IP (AR101 or matching placebo) at the site, with dosing beginning at 0.5 mg and progressing in graduated doses (if tolerated) of 1, 1.5, 3, and 6 mg. Following the first dose, subsequent doses will be delivered at 20 to 30 minute intervals. The schedule for initial day dose escalation is shown in [Appendix 1](#).
- Post-dose vital sign measurements (BP, pulse rate) at the following times:
 - Within 15 to 30 minutes post-dose,
 - At 30 minute intervals thereafter and for the duration of the post-dose observation period.

- Monitoring for AEs, including allergic symptoms (below and [Section 6.7](#) and [Section 7.2](#))
- Subjects will be reminded to continue to follow a peanut-avoidant diet for the duration of the study.

Subjects may have clear liquids or flavored gelatin during the day of the initial day escalation procedure while they are being given the desensitization doses.

At a minimum, subjects must be observed for 90 minutes after completion of dose escalation, with vital sign measurements and assessment for signs and symptoms of allergic reaction performed every 30 minutes. Any signs or symptoms of allergic reaction will be recorded in the case report form (CRF) on the appropriate Dosing Symptom/AE form.

- If Day 1 dose escalation is completed with no symptoms detected after 90 minutes of post-dose observation, the subject may be sent home from the CRC.
- If the subject exhibited **mild symptoms**, the duration of the observation period should be extended beyond 90 minutes, if applicable, so that the subject is observed for a minimum of 1 hour after resolution of the symptoms. Subject can continue in the study.
- For **moderate symptoms**, the observation period should be extended to a minimum of 2 hours after resolution of the symptoms. Subject is to be discontinued as an escalation failure.
- For **severe symptoms**, the subject should be observed for a minimum of 3 hours after resolution of the symptoms, either at the CRC or an emergency facility, as appropriate. Subject is to be discontinued as an escalation failure.
- Any subject deemed to have severe symptoms that include hypoxia, hypotension, or change in mental status, stage 3 anaphylaxis defined in [Appendix 3](#), or who receives intensive therapy (to be determined by the investigator, but may include such interventions as IV epinephrine, intubation, or admission to an intensive care unit) for an allergic reaction at any time should be discussed with the medical monitor and discontinued from the study.
- If DLS occur at or before the 3 mg single dose, there will be no further dosing of IP. The subject will be asked to return to the CRC 14 to 16 days following the last dose of IP to undergo an Early Discontinuation Visit ([Section 6.4](#)). The subject will continue to be monitored for safety until the Early Discontinuation Visit is completed or any ongoing AEs are resolved, whichever comes first.
- If no DLS occur during Day 1 dose escalation, or if DLS occur only with the 6 mg single dose, the subject is to return to the CRC on Day 2 to confirm the tolerability of a single 3 mg dose of IP.

6.3.2.2 Day 2

On Day 2, the next consecutive day following Day 1, a single confirmatory 3 mg dose will be administered under medical supervision in the CRC. The only exception to Day 2

immediately following Day 1 is when unforeseen circumstances (eg, an intercurrent illness) create a safety risk to provide the next dose, consistent with the rules for missed doses ([Section 6.8](#)). Should this occur, the investigator should discuss the case with the medical monitor prior to administering the next dose.

Subjects must be free from active wheezing, a flare of atopic disease (eg, atopic dermatitis), or suspected intercurrent illness prior to continuing with Day 2 of the initial dose escalation.

The following assessments/procedures will be performed:

- Concomitant medication update
- Symptom-directed physical examination
- Diet (food allergen exposure) history update
- Pre-dose vital sign measurement (BP, pulse rate, body temperature)
- PEFR (3 attempts are to be performed, and the best value taken). PEFR should, as far as possible, be measured at the same time of day at each visit (eg, morning, afternoon, evening)
- Oral administration of a single 3 mg dose of IP
- Post-dose vital sign measurements (BP, pulse rate) at the following times:
 - Within 15 to 30 minutes post-dose,
 - At 30-minute intervals thereafter and for the duration of the post-dose observation period.
- Monitoring for AEs, including allergic symptoms ([Section 6.7](#))
- Subjects will be reminded to continue to follow a peanut-avoidant diet for the duration of the study.

At a minimum, subjects must be observed for 90 minutes after dose administration, with vital sign measurements and assessment for signs and symptoms of allergic reaction performed every 30 minutes. Any signs or symptoms of allergic reaction will be recorded in the CRF on the appropriate Dosing Symptom /AE form.

- If Day 2 dosing is completed with no symptoms detected after 90 minutes of post-dose observation, the subject may be sent home from the CRC.
- If the subject exhibited **mild symptoms**, the duration of the observation period should be extended beyond 90 minutes, if applicable, so that the subject is observed for a minimum of 1 hour after resolution of the symptoms. Subject can continue in the study.
- For **moderate symptoms**, the observation period should be extended to a minimum of 2 hours after resolution of the symptoms. Subject is to be discontinued as an escalation failure.

- For **severe symptoms**, the subject should be observed for a minimum of 3 hours after resolution of the symptoms, either at the CRC or an emergency facility, as appropriate. Subject is to be discontinued as an escalation failure
- Any subject deemed to have severe symptoms that include hypoxia, hypotension, or change in mental status (stage 3 anaphylaxis defined in [Appendix 3](#)), or who receives intensive therapy (to be determined by the investigator, but may include such interventions as IV epinephrine, intubation, or admission to an intensive care unit) for an allergic reaction at any time should be discussed with the medical monitor and discontinued from the study.
- If DLSs occur on Day 2, there will be no further dosing. The subject will be asked to return to the CRC 14 to 16 days following the last dose of IP to undergo an Early Discontinuation Visit ([Section 6.4](#)). The subject will continue to be monitored for safety until the Early Discontinuation Visit is completed or any ongoing AEs are resolved, whichever comes first.
- Those subjects who tolerate the single 3 mg dose of IP on Day 2 will be dispensed a 2-week supply of IP at the 3 mg/d dose level. They will be instructed to continue daily oral dosing at home, starting the following day (Day 3), and to continue daily home dosing at that dose level for 2 weeks until next escalation.
- Subjects and parents/guardians will be educated on home dosing instructions per [Section 5.2](#).

On Day 3, the site is to make telephone contact with the subject/subject's parent or guardian to enquire if any AEs (including allergic symptoms) occurred subsequent to the subject leaving the clinic, and to provide assistance in recording of, and responding to, any such events.

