Based on experience from Phase 2 studies, most acute allergic responses to dosing that are characterized by mild symptoms would be anticipated to meet the above criteria. If, however, an allergic response to dosing is characterized by mild symptoms that do not meet all of the above criteria (eg, has mild symptoms occurring in 2 or more organ systems, requires treatment with 2 doses of antihistamine or 1 dose epinephrine, shows progression in severity or distribution over time, is protracted in duration, or includes objective wheezing), then even though the allergic symptoms may be mild, the dose should be assessed as not tolerated. If a dose elicits mild symptoms that do not fit all of the above criteria and the dose is assessed to

be tolerated, then a brief explanation as to why the dose was considered tolerated must be recorded in the CRF.

Moderate symptoms: In general, if a dose elicits moderate symptoms, the dose will be assessed as not tolerated. However, there may be rare occasions when a dose eliciting moderate symptoms could be assessed as tolerated. This would only be the case for a transient, self-limited (requiring no intervention and resolving completely) symptom occurring in a single organ system. In addition, the symptom would be typically subjective only. Any dose associated with moderate symptoms and assessed as tolerated must be accompanied by a brief explanation in the CRF as to why the dose was considered tolerated.

Severe symptoms: In nearly all cases, if a dose elicits severe symptoms, the dose will be assessed as not tolerated. Whenever a dose elicits an allergic response characterized by 1 or more severe symptoms, the crucial decision, after adequate treatment for the allergic reaction has been administered, will be to determine whether the subject should continue in the study, dosing at a reduced dose level, or be discontinued early from the study.

The determination of tolerability will decide the course of action to be taken in response to dose-related reactions ([Section 6.7.3](#)).

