In general, if a subject requires only 1 or 2 doses of antihistamine to treat mild symptoms occurring during the course of the initial escalation, then the initial escalation may continue. If, however, the subject requires a second medication (eg, epinephrine or a beta-agonist) to treat the symptoms, or more than 2 doses of an antihistamine, the initial escalation is to be terminated and the subject is to receive no further OIT, even if the symptoms were assessed to be mild. Use of epinephrine to treat dose-related symptoms, even in the unlikely event that the symptoms are graded as mild, will be cause to terminate the initial escalation.

Moderate symptoms: For moderate symptoms, if the symptoms are not worsening or amassing at a rapid pace, then a stepwise approach to treatment may be taken at the discretion of the investigator. If the first action undertaken is to implement an observation period, the observation period should not exceed 30 minutes before either the symptoms are noted to be resolving or therapy is instituted. Whether treatment is initiated immediately or after an observation period, the subject may be treated first with antihistamines or immediately with epinephrine, as deemed appropriate by the investigator. Other therapies may be added either sequentially or simultaneously, per investigator judgment.

If moderate symptoms occur at any of the doses below 6 mg (ie, up to and including 3 mg), then the desensitization procedure will be discontinued. The decision to discontinue escalation is to be based solely on the determination of whether the allergic reaction was of moderate severity. Although it is generally the case that some form of treatment will be instituted for moderate symptoms, treatment is not a requirement for assessing an allergic reaction as being of moderate severity.

Severe symptoms: For severe symptoms, the actions taken should be to discontinue the initial escalation and administer the appropriate rescue medications. The desensitization procedure will be discontinued regardless of the dose at which the severe symptom or symptoms occurred.

The medical monitor will answer any questions and assist in any decisions related to the study protocol.

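### Three dosing rules conflict, each at one boundary case: moderate symptoms only at 6 mg on Day 1, exactly 7 days missed for non-compliance, and exactly 4 consecutive missed doses in Up-dosing

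*Protocol*

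**What the plan says.** **(a) Moderate symptoms only at 6 mg on Day 1.** The moderate-symptom bullet of Protocol Section 6.3.2.1 extends observation "to a minimum of 2 hours after resolution of the symptoms. Subject is to be discontinued as an escalation failure". No dose is named. The last bullet of the same list says that "if DLS occur only with the 6 mg single dose, the subject is to return to the CRC on Day 2" to confirm 3 mg. Section 3.2 and the synopsis likewise send a child who tolerates 3 mg but not 6 mg to the Day 2 confirmation. Section 6.7.2 links the two bullets: "In general, if a dose elicits moderate symptoms, the dose will be assessed as not tolerated".

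Section 6.7.4 states its moderate-symptom stop for a limited range: "If moderate symptoms occur at any of the doses below 6 mg (ie, up to and including 3 mg". For severe symptoms it says: "The desensitization procedure will be discontinued regardless of the dose at which the severe symptom or symptoms occurred". The note to Table 1 also ties escalation failure to moderate or severe symptoms at 3 mg.

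**(b) Exactly 7 consecutive days missed for non-compliance.** Section 7.11.2 makes seven or more days a stopping rule. Section 4.3.1 and the non-compliance bullet of Section 6.8 stop only above 7. Section 6.8 restarts 5 to 7 missed doses at about 50% of the last tolerated dose.

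**(c) Exactly 4 consecutive missed doses in Up-dosing.** Section 7.11.2 requires a reduced restart dose once more than 3 days are missed. Section 6.8 has its own step for 4 doses: the current dose, supervised in the clinic.

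**The concern.** These are operative instructions that a site has to apply on the day, and the protocol sets no order of precedence among the sections. In cases (a) and (b) one section discontinues the child and another keeps the child in treatment. Under Section 9.2.1 a child who discontinues before the Exit DBPCFC is a treatment failure (Missing = Failure), so the choice of section can fix that child's primary outcome. Case (c) does not decide discontinuation. It decides the allergen dose given after a lapse, in the period where Section 6.8 itself places the highest risk from missed doses. What is at stake is uniform stopping and restart practice across sites.

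**Working it through.** The plan states no figure on this point, so the check sets the rules side by side.

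**Case (a): Day 1 symptoms by dose and grade**

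| Rule | Moderate, 3 mg or below | Moderate, 6 mg only | Severe, 6 mg only |
|---|---|---|---|
| 6.3.2.1 severity bullets | discontinue | discontinue | discontinue |
| 6.3.2.1 bullets on dose-limiting symptoms (DLS) | no further dosing | Day 2 | Day 2 if read literally |
| 3.2 and synopsis | failure (3 mg not tolerated) | Day 2 | severity not mentioned |
| 6.7.4 | discontinue | no explicit instruction; continuing by inference | discontinue |
| Table 1 note | failure if at 3 mg | not named; continuing by inference | not named |

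For moderate symptoms at 3 mg or below the rules agree. Severe symptoms at 6 mg are settled by two specific statements: the severe bullet of 6.3.2.1 ("either at the CRC or an emergency facility, as appropriate. Subject is to be discontinued as an escalation failure") and the dose-independent stop in 6.7.4. The conflict left is 1 of the 5 Day 1 doses at 1 of 3 symptom grades.

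**Cases (b) and (c): consecutive days missed in Up-dosing through non-compliance**

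| Days missed | Section 6.8 | Section 4.3.1 | Section 7.11.2 | Result |
|---|---|---|---|---|
| 1–2 | current dose, home | no stop | no rule | agree |
| 3 | current dose, clinic | no stop | no rule | agree |
| 4 | current dose, clinic | no stop | reduced dose | **conflict (c)** |
| 5–6 | about 50% | no stop | reduced dose | agree |
| 7 | about 50% | no stop | stop | **conflict (b)** |
| 8–9 | stop | stop | stop | agree |

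**Illustration of (b), for a child at 240 mg**

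- Section 7.11.2: no further dose.
- Section 6.8: 0.50 × 240 = 120 mg, which is a Table 2 level. The return path is 120 → 160 → 200 → 240, so 3 one-level increases.
- At no more than one increase a week: 3 × 1 = 3 weeks at least. At the general limit of one every 4 weeks: 3 × 4 = 12 weeks.

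For (c) no dose ratio can be given, because Section 7.11.2 does not state the size of the reduction.

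**The case against.** The best counter-argument concerns (a). Section 6.7.4 does not say that moderate symptoms stop the child only at 3 mg or below; it gives no instruction for moderate symptoms at 6 mg. The moderate bullet of 6.3.2.1 could be read as filling that silence, and the last bullet as covering only mild symptoms judged dose-limiting. A reader might infer that 6.7.4 flatly contradicts 6.3.2.1. The text does not go that far. The contrast with the severe-symptom rule supports continuing, but by inference. Even so, the mild-only reading does not remove the conflict with Section 3.2 and the synopsis, which send children who tolerate 3 mg but not 6 mg to Day 2 without a severity limit. Figure 2, the Day 1 algorithm, is not available in the text and is not relied on; it might show the intended rule, but the written sections would still differ.

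A reader might also infer that the treatment-based stops in 6.7.4 already govern moderate reactions at 6 mg: "or more than 2 doses of an antihistamine, the initial escalation is to be terminated and the subject is to receive no further OIT", and, for epinephrine, "even in the unlikely event that the symptoms are graded as mild, will be cause to terminate the initial escalation". Both sentences sit in the discussion of mild symptoms, and the moderate paragraph bases its decision solely on severity. Carrying them over is a clinical interpretation.

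On (b), 4.3.1 and 6.8 agree and 7.11.2 is the outlier. On (c), the step in 6.8 is explicit. That shows which text to correct, not that the conflict is absent. Section 7.11.2 also omits the word consecutive for the 3-day threshold. The single-point description of (c) therefore assumes consecutive days, although 4 consecutive days exceeds 3 on any reading.

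The mitigating facts stand: the Section 6.8 restarts in question are supervised in the clinic, and a medical monitor can be consulted.

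**Conclusion.** The point holds as a minor drafting defect. Cases (b) and (c) are direct contradictions between stated thresholds. Case (a) is a conflict between the moderate bullet of 6.3.2.1 on one side and the last bullet of 6.3.2.1 with Section 3.2 on the other; 6.7.4 and the Table 1 note support continuing by inference. Each conflict occupies one case: moderate symptoms at one dose, day count 7, and day count 4 (read as consecutive).

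A reader might infer a biased treatment comparison or a loss of power because Missing = Failure applies. The documents do not support that. The rules are applied blinded in both arms, the number of children at these boundaries is not given and is probably small, and no effect on the response rate can be calculated. The conclusion is limited to inconsistent stopping and restart instructions across sites.

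**What to change.** - **(a)** In 6.3.2.1, limit the moderate-symptom discontinuation to doses at or below 3 mg, and state in the last bullet that severe symptoms at 6 mg still discontinue. If the stricter rule is intended, amend the last bullet, 6.7.4, Section 3.2 and the synopsis together. Whether epinephrine, a second medication or more than 2 antihistamine doses at 6 mg should also stop a child is a clinical choice. If adopted, it must appear in all of these sections.
- **(b)** In 7.11.2, change the non-compliance threshold from seven or more days to more than 7. If the stricter rule is chosen, change 4.3.1 and the non-compliance stop in 6.8 to 7 or more, but keep 7 days in the 6.8 restart band for product withheld for an AE or a dispensing error. The separate band for those reasons starts at 8 days, so shortening the general band to 5–6 would leave day 7 without a restart rule.
- **(c)** In 7.11.2, change the reduced-dose threshold from more than 3 days to 5 or more consecutive days, matching 6.8.

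The cost is a few sentences of protocol wording and a site memo, with the amendment approvals that Section 11.1 requires. No subjects, visits or procedures are added.

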If a subject discontinues therapy prematurely for any reason, the subject will be followed for safety and asked to return to the CRC 14 to 16 days following his or her last dose of IP to undergo an Early Discontinuation Visit ([Section 6.4](#)). In the event of ongoing AEs, subjects who have discontinued therapy should continue to be followed beyond the Early Discontinuation Visit until such time as the AE has resolved or is assessed to have reached a chronic stable state (a determination that may not be made sooner than 30 days after the Early Discontinuation Visit). Subjects who have GI AEs with prolonged disruption of dosing or who discontinue treatment due to GI AEs will have safety follow-up for 6 months or until chronic or recurrent GI symptoms resolve or stabilize, whichever is last ([Section 7.3.3.2](#)).

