4.3.2 Follow-up of Subjects Who Discontinue Treatment

If a subject discontinues therapy for any reason, the subject will be followed for safety and asked to return to the CRC for an Early Discontinuation Visit 14 to 16 days after their last dose of IP. To the extent possible, subjects will be monitored for safety until they come back for their Early Discontinuation Visit.

In the event of ongoing AEs, subjects who have discontinued therapy should continue to be followed beyond the Early Discontinuation Visit until the AE has resolved or is assessed to have reached a chronic stable state (a determination that may not be made sooner than 30 days after the Early Discontinuation Visit).

Subjects who have GI AEs with prolonged disruption of dosing or who discontinue treatment due wholly or in part to GI AEs will have safety follow-up for 6 months or until chronic or recurrent GI symptoms resolve or stabilize, whichever is last, and be instructed to complete the Pediatric Eosinophilic Esophagitis Symptom Scores (PEESS™ v2.0) questionnaire (Franciosi et al, 2011) at the time of treatment discontinuation and monthly for 6 months (Section 7.3.3.2). Additional instructions for the follow-up of subjects who discontinue treatment due wholly or in part to GI AEs are provided in Section 7.3.3.2.

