7.3.3.2 Gastrointestinal AEs Resulting in Prolonged Disruption of Dosing (Events of Interest)

Gastrointestinal AEs, typically chronic/recurrent GI AEs, that result in a prolonged disruption of dosing will be considered AEs of interest (AEIs) and will be assessed longitudinally according to the procedures described below. For the purpose of delineating these AEIs, prolonged disruption of dosing is defined as withholding IP for > 7 days. This will include 3 categories of subjects:

- Any subject whose dose is withheld for > 7 days due to GI AEs and resumes dosing at a reduced dose level ([Section 6.7](#))

- Any subject who develops chronic/recurrent GI AEs at or before reaching the 20 mg dose level and resumes dosing after a 30-day dosing hiatus ([Section 6.7.3.2](#));
- Any subject who permanently discontinues dosing due to GI AEs ([Section 4.3.1](#)).

Subjects who fall into any of these 3 categories will be asked to fill out the PEESS v2.0 questionnaire, with the assistance of a parent or guardian, as appropriate, while symptomatic, at the time of treatment discontinuation, and then every month for 6 months thereafter. During the 6-month safety follow-up, subjects may complete the PEESS v2.0 at home and send it to the clinic, or they may complete it at the clinic if monthly clinic visits are required.

It should be noted that the PEESS v2.0 was not designed to establish a diagnosis of EoE, and has not been validated for use in subjects with GI symptoms of other etiologies. Furthermore, the discriminant validity of the questionnaire has not been reported in either longitudinal natural history or interventional studies. For these reasons, the use of the PEESS v2.0 to monitor the clinical course of GI symptoms must be considered exploratory. Nevertheless, the PEESS v2.0 has shown good content and construct validity ([Franciosi et al, 2011](#); [Martin et al, 2015](#)) and so holds promise for being a valuable tool to follow the clinical course of EoE or an EoE-like immune-mediated GI syndrome. Thus, the PEESS v2.0, could reveal trends toward symptomatic improvement or worsening that might otherwise go undetected.

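### Sections 6.3.2.1 and 6.3.2.2 let safety monitoring of initial-escalation failures end at the Early Discontinuation Visit even with an AE still open, contradicting the post-visit follow-up in 3.2, 4.3.2 and elsewhere

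*Protocol*

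**What the plan says.** Under Protocol 6.3.2.1, a subject with dose-limiting symptoms at or before the 3 mg dose on Day 1 receives no more study product and returns 14 to 16 days after the last dose for the Early Discontinuation Visit. Section 6.3.2.2 says the same for dose-limiting symptoms on Day 2. Both then continue safety monitoring "until the Early Discontinuation Visit is completed or any ongoing AEs are resolved, whichever comes first".

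The general rule in 3.2 reads: "If a subject discontinues therapy prematurely for any reason, the subject will be followed for safety". For AEs that are still ongoing it adds that "subjects who have discontinued therapy should continue to be followed beyond the Early Discontinuation Visit until such time as the AE has resolved" or the AE is judged chronic and stable. Section 4.3.2 repeats this and describes the stability judgement as "a determination that may not be made sooner than 30 days after the Early Discontinuation Visit".

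For GI events, 4.3.2 states that subjects "who discontinue treatment due wholly or in part to GI AEs will have safety follow-up for 6 months". That period is a minimum: where chronic or recurrent symptoms take longer to settle, follow-up lasts until they have done so. The PEESS v2.0 questionnaire is completed "at the time of treatment discontinuation and monthly for 6 months". Section 7.3.3.2 lists three categories of GI event of interest. The third is "Any subject who permanently discontinues dosing due to GI AEs".

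Section 6.4 and Appendix 1 note c both place subjects who fail initial escalation in the Early Discontinuation Visit group.

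**The concern.** The two sets of instructions cover the same children and cannot both be followed when an AE is open at the Early Discontinuation Visit. A site working from the initial-escalation section is told it may stop at that visit. A site working from 3.2 or 4.3.2 carries on. No text exempts initial-escalation failures from the general rule or says which section prevails.

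At stake are the consistency and completeness of safety follow-up in subjects who reacted at very low doses, some with severe symptoms. Demonstrating safety is a secondary objective (2.2). Sites could differ in how long they follow an open AE and in whether they start the longer GI follow-up. That divergence is an inference from the text; the protocol gives no data on it.

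**Working it through.** The plan gives no figure to reproduce. The check compares the sections and adds up the visit windows.

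**Same subjects?** Yes. Section 3.2 applies to premature discontinuation for any reason, and 4.3.2 to discontinuation for any reason. Section 6.4 and note c name initial-escalation failures explicitly.

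**Is 6.3.2 the outlier?** Yes.
- 6.3.3.1, 6.3.4, 6.7.6 and 6.8 order the same 14-to-16-day visit without this cut-off. Section 6.3.3.1 asks only for safety follow-up in the interim.
- 7.4.1 also sets an end at the visit, but then says that AEs ongoing when study product stops may need additional monitoring after it.
- 7.8 sets a default end of 30 days after treatment, and requires additional visits after the Early Discontinuation Visit when an ongoing AE cannot yet be called stable.
- Appendix 1 note w gives subjects with ongoing AEs at early discontinuation at least 30 days of follow-up, or until resolution or stabilization if later.
- The sentences in 6.3.2.1 and 6.3.2.2 carry no such override.

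**Timeline, with the last dose as day 0**

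| Situation | End under 6.3.2 | End under 3.2 / 4.3.2 |
|---|---|---|
| AE open at the visit | day 14 to 16 | resolution, or a stability call no earlier than day 44 to 46 |
| GI discontinuation, if the GI rule covers acute reactions | day 14 to 16 at the latest | about day 183 at the earliest |

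*Open AE.* The visit is at day 14 to 16. The earliest stability call is 14 + 30 = day 44 to 16 + 30 = day 46. The gap is 44 − 14 = 30 days, or 46 − 16 = 30 days. It is shorter if the AE resolves first: one resolving on day 17, after a visit on day 16, leaves a gap of 1 day.

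*GI discontinuation (conditional).* Assume months of 30.44 days counted from the last dose. Then 6 × 30.44 = 182.6, about day 183. The gap is 182.6 − 16 = 166.6 to 182.6 − 14 = 168.6, so about 167 to 169 days. This is a minimum, because 4.3.2 takes the later of its two end points. PEESS v2.0 is completed once at discontinuation and six times monthly, 7 in all. The first monthly completion falls at about day 30, so 6 of the 7 come after day 16.

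**Does the GI rule reach these subjects?** Literally, it can. Section 4.3.2 refers to GI AEs as all or part of the reason for stopping, and the third category in 7.3.3.2 is not limited to chronic or recurrent events. Section 6.7.1 grades repeated vomiting or diarrhea as moderate, and 6.3.2 discontinues subjects with moderate symptoms.

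**The case against.** The strongest reply is that the longer follow-up does reach the site. Section 6.1 sends sites to Appendix 1 for procedures. There, the AE-monitoring row carries note w in the Early Discontinuation column, and note w refers to both 4.3.2 and 7.3.3.2. With 7.4.1 and 7.8 also providing for post-visit follow-up, the 6.3.2 sentence looks like a slip of wording. A reader might infer that the sponsor means to drop follow-up of escalation failures; the documents do not support that. But none of these sections cancels the 6.3.2 instruction. The 6.3.2 sentences point only to 6.4, and the AE item in 6.4 points to 6.7 and 7.2, not to 4.3.2.

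The objection to the GI part is stronger. A reader might infer a flat contradiction with the 6-month rule. Section 7.3.3.2 is headed as concerning prolonged disruption of dosing and describes these events as typically chronic or recurrent. It asks for monthly clinic return only after chronic or recurrent GI AEs. The end point in 4.3.2 is also worded for chronic or recurrent symptoms, and 6.7.3.2 separates these from acute dosing reactions. A reaction within two dosing days is acute. Whether it triggers the 6-month rule is therefore arguable, and the 167 to 169 days hold only on the literal reading.

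Exposure is also likely to be small. Section 6.3.2 requires at least 2 hours of observation after moderate symptoms resolve and 3 hours after severe ones, so most index reactions should be over on the dosing day.

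Finally, a reader might infer a loss when the AE resolves before the visit, since 6.3.2 then ends monitoring at resolution while 4.3.2 says "To the extent possible, subjects will be monitored for safety until they come back for their Early Discontinuation Visit". No named procedure is lost: the visit still takes place, and the diary and AE recording through the visit (7.4.1) cover the interval.

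**Conclusion.** The contradiction is established for an AE still open at the Early Discontinuation Visit. Section 6.3.2 permits monitoring to stop at day 14 to 16, whereas 3.2 and 4.3.2 continue to resolution or to a stability call no earlier than day 44 to 46. The 30-day difference is not a fixed shortfall; it applies when the AE has not resolved by then. The GI conflict is conditional on the literal reading of 4.3.2 and 7.3.3.2.

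The number of subjects affected cannot be derived, because the protocol gives no count of initial-escalation failures or of AEs open at the visit. It is probably small.

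A reader should not infer any effect on the efficacy conclusions. These subjects count as treatment failures under 9.2.1 however long they are followed, so the primary endpoint, power and type I error are unchanged. The point is worth correcting because the sentence is an operative safety instruction for children who reacted during initial escalation.

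**What to change.** In both 6.3.2.1 and 6.3.2.2, replace the sentence with:

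> Monitor the subject for safety up to and including the Early Discontinuation Visit. Follow AEs ongoing at that visit per Section 4.3.2, and GI AEs leading to discontinuation per Sections 4.3.2 and 7.3.3.2 where those apply.

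This costs two replaced passages and adds no procedure beyond those already in 3.2, 4.3.2 and 7.3.3.2. The closing qualifier leaves open whether an acute GI reaction on a dosing day starts the 6-month follow-up; if the sponsor wants that settled, 4.3.2 is the place to say so.
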